## STUDY SYNOPSIS

Sponsor person	[name]. med. [name]
Study title:	INDIVIDUAL BALANCE TRAINING VS. GROUP BALANCE TRAINING TO IMPROVE WALKING SPEED POST STROKE- A RANDOMIZED, CONTROLLED PILOTSTUDY
Protocol version and date:	Vers. 2.0, 20.11.2018
Registry:	Swiss Clinical Trials Portal Clinicaltrials.gov
Category:	Other clinical trial category A
Background and Ratio:	
The RehaClinic Kilchberg is a neurological rehabilitation facility with the phases B-D (after Schönle 1996). Between February and the end of March, out of 78 patients, 71% had stroke patients. Therefore, my choice of topic for the Master's thesis fell on the stroke. The duration of the study is based on the timetable for the Master's thesis. Initially, 20 stroke patients will be recruited. When the number is reached, the study is completed to begin descriptive statistics and analyze potential BIAS.
 
The primary goal of the study is to determine if there is a difference in effect size when comparing individual balance training to group balance training. Since only 7% of inpatient rehabilitation patients were able to climb stairs at discharge and had reached sufficient walking speed to be safe and independent in everyday mobility (Balasubramanian, Clark, & Fox, 2014), the primary outcome is walking speed. It is determined with the 10m walk test. The secondary outcome of balance is captured by the Berg Balance Scale. The ability to walk is determined by the functional ambulation categories (FAC).
 
Deficits in the vestibular, visual, motor, and / or somatosensory systems lead to falls in the first 6 months after the stroke. This affects approximately 46% of patients (Mackintosh, Hill, Dodd, Goldie, & Culham, 2005). But also cognitive processes, such as attention and concentration. Therefore, the treatment must be adapted to the respective strategy of the patient. If the patient increasingly uses the visual system, the therapy has to work a lot with the eyes closed. In turn, if he uses more of the sensory motor system is increasingly trained with unstable documents (Mehrholz, Ada, Dean, Dettmers, & Dohle, 2011). After this system, the balance program was set up. It is the same for the intervention and control group to make a difference between individual and group training.

Goal:	
Goal: A suitable sample size is to be determined for a larger follow-up study and the study design should be checked for feasibility.
 
Question: In stroke patients, is there a difference between individual and group balance training in terms of improving walking speed?
 
Hypothesis: individual balance training has a better impact on walking speed than group balance training.
 
Primary outcome: gait speed → 10m walking tests
 
Secondary outcome: Berg-Balance Scale, FAC

Participants:	It will recruit 20 patients after stroke at the RehaClinic Kilchberg.
Study design:	controled, randomized, open pilot study with paralell groups - monocentric
In/Exclusion criteria:	Inclusion: min. 18 years, stroke starting from rehabilitation phase B, ability to understand therapy instructions, walkable with aids Exclusion: Neurodegenerative disease, non-stroke dizziness, cardiopulmonary insufficiency, polyneuropathy, peripheral vascular disease
Experimental intervention:	individual balance training: after the initial assessments, the three week intervention time begins, which is completed with the reassessments.  The patients receive 2x weekly individual balance training for 25 minutes each.  This runs in addition to the normal, prescribed rehabilitation program. The rehabilitation program includes at least 3 therapies daily. These may be group therapies, speech therapy, occupational therapy, neuropsychology and physiotherapy adapted to the needs of the patient. In physiotherapy and occupational therapy no balance training may be performed during the intervention period.
Controle intervention:	The patients receive 2x weekly group balance training for 25 minutes each.  This runs in addition to the normal, prescribed rehabilitation program. The rehabilitation program includes at least 3 therapies daily. These may be group therapies, speech therapy, occupational therapy, neuropsychology and physiotherapy adapted to the needs of the patient. In physiotherapy and occupational therapy no balance training may be performed during the intervention period.  In group therapy are 3 to 6 patients with different neurological diagnoses. As it is usual in rehabilitation everyday life.
Number of participants:	In total, 20 patients should be recruited. 10 in the intervention group and the other half in the control group.
Study period:	It will start as soon as possible after the positive decision of the ethics committee. Expected on 07.01.2019. The last patient will complete the intervention on 26.04.2019. The positive decision of the ethics committee arrived at 19.12.2018.

Timeplan:	
 
▪ I check the submitted reports one day before arrival, if the patient is suitable and inform the doctors (head doctor, senior physician and assistant doctors of the ward)
 
▪ The doctors check this again on the admission day and give me feedback
 
▪ I go to the patient on the second day and inform him / her about the ongoing study and give him / her the consent
 
▪ If the patient has signed, the berg balance scale and the 10m walk test will be performed on the same or the next day and the envelope will be drawn for randomization.
 
▪ Then he will be assigned at the next opportunity so that he gets the balance training twice a week
 

Investigator:	
[name], Physiotherapist, BA  [name], [name], Switzerland  [contact]  [name]

Study location:	
RehaClinic Kilchberg, [name], [name], Switzerland

Statistic Analyses:	
It is applied by the low descriptive statistics record and the SampleSize is determined. It uses SPSS version 25 and G * Power Vers. 3.1.9.2

GCP:	
This clinical trial will be conducted in compliance with the protocol, the current version of the Helsinki Declaration and ICH-GCP, as well as national guidelines and legislation.

# LIST OF ABBREVIATIONS

BBS	Berg Balance Scale
CRF	Case Report Form (Prüfbogen)
IB	Individual balance
eCRF	Electronic Case Report Form (elektronischer Prüfbogen)
FAC	Functional ambulation categories
GB	Groupbalance
GCP	Good Clinical Practice (Gute Klinische Praxis)
ICH	International Council on Harmonization
ISF	Investigator Site File/Prüfzentrums-Ordner
SAE	Serious Adverse Event
SDV	Source Data Verification
SNCTP	Swiss National Clinical Trial Portal
SOP	Standard Operating Procedure
TMF	Trial Master File

# VISITATION PLAN

Testplan periode	Screening	Treatment periode							Follow-up
week	-1 bis 1	1	1-2	2	2	2-3	3	3	3 until rehabilitati on ends
Visitation	1	2	3	4	5	6	7	8	9
Participant information and consent	x								
Demografic Data	x								
Anamnese	x								
In-/Exclusion	x								
Physical examinaton	x								x
Vital signs	x	x	x	x	x	x	x	x	x
Laboratory	x								x
Randomisation	x								
Assessments	x								x
Testintervention	(x) Je nach Anreisetag	x	(x)	x	x		x	x	
Medication	x	x	x				x	x	x

### 1.3 Statistics/Biometrics

It is applied by the low descriptive statistics record and the SampleSize is determined. It will be use SPSS version 25 and G \* Power Vers. 3.1.9.2

## 2 ETHICS UND REGULATORY ASPECTS

Before proceeding with this study, in accordance with local regulatory requirements, the protocol, the patient information draft and consent form, together with the other study-specific documents, should be sent to a properly composed, competent ethics committee for formal trial approval.

The decision of the competent ethics committee regarding the conduct of the study will be communicated to the sponsor examiner in writing before the beginning of the experiment. The clinical trial may begin only after approval by the EC has been obtained. Registrierung

Die Pilotstudie wird im Swiss Clinical Trials Portal registriert.

### 2.1 Study category

**Category A:** *The examined health-related intervention is associated with only minimal risks and burdens.*

### 2.2 competent Ethic commission (EC)

*For the clinical trial, the approval of the properly composed competent ethics committee will be obtained. The reporting obligations and the prescribed time windows are adhered to. No significant changes will be made to the protocol without the prior approval of the sponsor and the Competent Ethics Committee. Excluded are situations in which immediate danger is to be averted from the participating persons.*

*A planned termination of the trial must be reported to the EC within 90 days, premature termination or interruption within 15 days. The final report must be submitted within one year after the end of the clinical trial. Amendments are to be reported according to chapter 2.9.*

### 2.3 Conduct the studies according to ethical guidelines

This study is conducted in compliance with the principles outlined in the current version of the Helsinki Declaration, in accordance with Good Clinical Practice (GCP) issued by the International Committee for Harmonization (ICH), as well as Swiss legislation.

The Ethics Committee will be informed in accordance with local requirements with annual safety reports and interim reports of any other changes, the course of the clinical trial, and the end / stop of the trial.

## **2.4 Declaration of Interest**

*It states that there are no competing interests and intellectual, financial and copyright independence is respected.*

## **2.5 Participant information and consent**

The investigator must explain to each participant the nature and purpose of the clinical trial, the intended actions, the likely duration, the benefits and possible risks, and any inconvenience this may cause. Each participant must be informed that participation in a clinical trial is voluntary, that he / she may terminate the activity at any time, and that withdrawal of the consent will not interfere with his / her subsequent medical treatment / care.

The study participant must be informed that his / her medical records can be inspected by other, authorized persons in addition to the attending physician.

All study participants will be provided with participant information and a declaration of consent, which describes the study and contains sufficient information so that the participants can make an informed decision about their study participation.

The participant information and informed consent will be presented together with the study protocol for review and approval by the Competent Ethics Committee and Swissmedic. The formal consent of a participant must be obtained before the participant participates in any study activity. The approved consent form must be used for this purpose.

The participant should read and rethink the information before signing and dating the consent form. The consent form must also be signed and dated by the investigator or his deputy and kept as part of the study documentation.

## **2.6 Confidentiality of the subscriber data**

The investigators are responsible for ensuring that all study-related information and data collected are kept strictly confidential. Any transfer of information to persons who are not directly involved in the study must be approved by the owner of the data.

Data collection, dissemination, archiving and analysis of personal data within the study are strictly based on the valid Swiss data protection regulations. The prerequisite for this is the voluntary approval of the test participants, which is given by signing the declaration of consent before participating in the clinical trial.

Personal medical information of a participant obtained in the study should be considered confidential and disclosure to third parties is prohibited. Confidentiality is further ensured through the use of subscriber identification numbers (IDs) associated with the electronically stored treatment data.

If the participant has given their written consent, this medical information may be passed on to the family doctor or other treating physicians to ensure the well-being of the subject.

The data collected during this clinical trial are available for review or inspection by monitors and the independent EC.

## **2.7 Premature termination of the experiment**

Under the following conditions, the sponsor investigator may terminate the clinical trial prematurely:

- ethical concerns,
- insufficient patient recruitment,
- if the safety of the participants is doubtful or endangered,
- Change in accepted clinical practice, which would make it unwise to continue the experiment
- Achieving a positive or negative result earlier than expected.

## **2.8 Protocol amendments**

Significant amendments are only to be implemented after approval by the competent Ethics Committee.

For the competent ethics committee are considered substantial changes:

- changes affecting the safety and health of the participants or their rights and obligations;
- Amendments to the control plan, including changes due to new scientific knowledge, including the experimental design, the test method,
- concern the target criteria or the statistical evaluation concept;
- the change of the place of performance or the conduct of the clinical trial at an additional site; or
- the change of the sponsor, the coordinating investigator or the investigator responsible at a place of performance.

In emergency situations, without the consent of the sponsor, the ethics committee may be waived from the protocol to ensure the rights, safety and well-being of the participants. These deviations must be documented as soon as possible and reported to the sponsor and the ethics committee. All non-essential Amendments are to be notified to the Ethics Committee with the annual safety report.

### **3 INTRODUCTION**

Every year, around 16,000 Swiss people a stroke (Meyer, Simmet, Arnold, Mattle, & Nedeltchev, 2009). This leads to the interruption of the blood supply in the brain. This can be caused on the one hand by an ischemia, or by a rupture of a blood vessel (World Health Organization, 2016). This often leads to limitations in everyday activities (Busch & Kuhnert, 2017). This is the main goal of the patient's treatment goals (Bohannon, Andrews, & Smith, 1988).

A 2014 review found that as many as 7% of inpatient rehabilitation patients were able to go upstairs on discharge and had reached sufficient walking speed to be safe and independent in everyday mobility (Balasubramanian, Clark, & Fox, 2014). In another study, 39% of stroke survivors fell (Nyberg & Gustafson, 1995).

Strokes often affect the exact systems we need for standing and aisle safety. According to Mehrholz et al. (2011) these are the vestibular, the visual, the motor and the somatosensory system. But also cognitive processes, such as attention and concentration play an important role here. Therefore, it seems likely that single-balance training is more efficient to improve walking speed. There is less distraction, with 55% of stroke patients complaining of lack of concentration (Hochstenbach, Prigatano, & Mulder, 2005), and individual instruction and external feedback promoting and supporting patient autonomy (Wulf, 2011)

In the reviews by Pollock et al (2014) or also by Dohle et al. (2016), different treatment approaches are analyzed and compared. So far, however, it has not been examined whether there is an effect difference in the intervention itself, whether this is done in individual or group settings. Therefore, in this pilot study, group balance training will be compared to single-weight training (Dohle, et al., 2016).

Therefore, a pilot study will be carried out to determine the feasibility of an RCT. This will reveal BIAS and determine the SampleSize needed to get a meaningful result.

#### **3.1 Background and Ratio**

The RehaClinic Kilchberg is a neurological rehabilitation facility with phases B-D. Between February and the end of March, out of 78 patients, 71% were stroke patients. Therefore, my choice of topic for the Master's thesis fell on the stroke. Sufficient patients should be recruited for the study period from July to the end of September. The duration of the study is based on the timetable for the Master's thesis. Initially, 20 stroke patients will be recruited. Once the number has been reached, the study is completed in order to be able to start with the descriptive statistics and to analyze potential BIAS.

The main purpose of the study is to determine if there is a difference in effect size when comparing single-balance training to group-balance training. Since only 7% of inpatient rehabilitation patients were able to climb stairs at discharge and had reached sufficient walking speed to be safe and independent in everyday mobility (Balasubramanian, Clark, & Fox, 2014), the primary outcome is walking speed. It is determined with the 10m walk test. The secondary outcome of balance is captured by the Berg Balance Scale. The ability to walk is determined by the FAC.

Deficits in the vestibular, visual, motor, and / or somatosensory systems lead to falls in the first 6 months after the stroke. This affects approximately 46% of patients (Mackintosh, Hill, Dodd, Goldie, & Culham, 2005). But also cognitive processes such as attention and concentration play an important role. Therefore, the treatment must be adapted to the respective strategy of the patient. If the patient increasingly uses the visual system, the therapy has to work a lot with the

eyes closed. In turn, if he uses more of the sensorimotor system is increasingly trained with unstable documents (Mehrholz, Ada, Dean, Dettmers, & Dohle, 2011). After this system, the balance program was set up. It is the same for the intervention and control group to make a difference between individual and group training. The group size results from the specification of the RehaClinic Kilchberg with a number of participants between 3-6 patients. The group will not exclusively include stroke patients, since the participants in rehabilitation routine are otherwise mixed up by the diagnoses. In most cases, stroke, Parkinson's, craniocerebral trauma and also tumor patients participate.

### **3.2 Experimental intervention und Indication**

The intervention is the balance training. It is carried out by me, or by a trained employee, in the case of my absence. There is a schedule for this, which I attach with. It is standing balance training in a safe setting. So nearby a bar. It is worked with different sized support surfaces. In each position you work with closed eyes and also with head rotation. Patients should be encouraged to take a protective step if they feel they are unbalanced. This balance program is standard in our rehabilitation clinic.

### **3.3 Clinical data and experience**

My Master's thesis is mainly about a feasibility study in order to be able to conduct an RCT on the subject. The required number of patients should be determined in order to obtain a meaningful result. Any occurring BIAS should be discussed and solutions found.

The walking speed and fall risk of stroke patients are determined from the moment of walking in a neurological rehabilitation clinic.

### **3.4 Justification of the experimental intervention**

The individual balance training will take place twice a week. This is sufficient to improve the balance (Mehrholz, Ada, Dean, Dettmers, & Dohle, 2011). The time is determined by the hospital setting. The effective practice time will be 25 minutes per balance unit, with a 30 minute clocking. Before the first intervention and after the 6th (last) the assessments are tested. During the intervention period, no balance training will be carried out in the other individual therapies or even in the group. The intervention takes place in addition to the normal therapy sessions.

### **3.5 Justification for the choice of the comparison intervention**

In the reviews by Pollock et al (2014) or also by Dohle et al. (2016), different treatment approaches are analyzed and compared. So far, however, it has not been examined whether there is an effect difference in the intervention itself, whether this is done in individual or group settings. Therefore, the control group will participate in the group balance. The process will take place exactly the same as in single-balance training. Again, may be performed in the other individual therapies and not in the group. The group balance training takes place in addition to the normal therapy sessions.

### **3.6 Risk / benefit analysis**

There is hardly an additional risk, because the balance training in the RehaClinic Kilchberg is always carried out in this way. Patients are assigned, after routine analysis, fitness for training, assessments and clinical observation of the balance group. Eventually, the additional therapy unit could cause fatigue. In order to reduce the risk of falling is trained nearby the bar, where the participants can hold if necessary.

The participants could be further promoted as they receive more therapy than intended.

Randomization does not disadvantage anyone in one of the groups (intervention / control).

At least three times a week the medical visit takes place during which patients can address questions or problems.

### **3.7 Participants**

Stroke patients who are at least 18 years of age, are capable of judgment and do not need a legal representative are recruited.

## **4 GOAL OF THE STUDY**

### **4.1 maingoal**

The study is part of my master thesis. But it has found so much interest in my superiors that they would possibly perform as a larger-scale RCT. Therefore, it is designed as a pilot study to detect any occurring BIAS and to be able to calculate a sample size, which will be necessary to be able to make a statement.

### **4.2 Primary goal**

Improvement of walking speed in stroke patients in inpatient rehabilitation through balance training. Determine if there is a difference in effect size between individual and group balance training.

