## **5 TARGETS OF THE STUDY**

### **5.1 Primary target**

Improving walking speed by 18 cm/sec would be a successful outcome (Fulk et al, 2011). Whether there is a difference between individual balance training and group balance training is to be determined. To be able to cross a pedestrian traffic light, a walking speed of 1.0-1.2 m/sec would be necessary (Hüter-Becker, et al., 2005). This would be the ideal value.

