## 7.5 General

### Standard therapy

According to the payer, the therapy is individually composed of the following therapies:

Individual Therapies: Speech Therapy (45min), Physiotherapy (30-45), Occupational Therapy (30-45), Neuropsychology (30-180), Physical Therapy (30-60)

Group therapies: Seating group (30), MTT (60), endurance group (45), self-training (30), water aerobics (30), fine motor skills (45), memory group (45), public transport group (135), cooking group (150), arm-hand Group (45), Household Group (45)

Of these, 3-4 therapies are selected Monday-Friday.

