## **7.5.2 Controle intervention**

### **Group balance training (GB)**

The exercise sequence is the same as IB training.

There will be between 3-6 patients. These may have different diagnoses and will not all have a stroke as a basic diagnosis.

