### 8.2.1 Recording of the primary target

The walking speed is tested one day before the first IB or GB and one day after the last IB / GB. So a training effect that could falsify the result should be avoided. It is measured by a physiotherapist.

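### Before-after gain in walking speed (4.2, 5.1) cannot be attributed to balance training, because both arms receive the same training; the individual-versus-group contrast is unaffected

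*Combined protocol and SAP*

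**What the plan says.** The primary goal in section 4.2 has two parts. The first is "Improvement of walking speed in stroke patients in inpatient rehabilitation through balance training". The second is "Determine if there is a difference in effect size between individual and group balance training".

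Section 5.1 does the same in a different form. It says "Improving walking speed by 18 cm/sec would be a successful outcome", and then, as a separate statement without a threshold, "Whether there is a difference between individual balance training and group balance training is to be determined". It does not say whether the 18 cm/s applies to a patient, an arm mean, the pooled mean or a difference between arms.

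On timing, section 8.2.1 states: "The walking speed is tested one day before the first IB or GB and one day after the last IB / GB".

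On the comparator, section 7.5.2 says of group training: "The exercise sequence is the same as IB training". Section 3.1 gives the reason for using one programme: "It is the same for the intervention and control group to make a difference between individual and group training". Both arms have six units of 25 minutes (7.6.1, 7.6.2), and in both these come on top of usual rehabilitation (3.4, 3.5). The synopsis puts usual rehabilitation at a minimum of three therapies a day. Section 7.5 lists the options and adds: "Of these, 3-4 therapies are selected Monday-Friday".

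The question and hypothesis in the synopsis, and section 10.1, concern individual versus group training only. The only between-arm statistic named in section 10 is an odds ratio, and no binary outcome is defined for it.

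**The concern.** The first part of the goal is causal: it credits a gain in walking speed to balance training. Showing that would need patients who did not have balance training, and the trial has none. The one factor that differs by randomisation is the setting, individual or group.

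The 18 cm/s target adds to the difficulty. Speed is measured before and after the programme, and the target is worded as an improvement, so it is naturally read as a before-after gain. Such a gain also includes the effect of the other therapies, any recovery over about three weeks, and repeat testing. If it were reported under the goal as now worded, the master's thesis and the planning of the follow-up trial could carry a statement about the training that the data cannot support.

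**Working it through.** **The plan's own figures.** The threshold is 18 cm/s = 0.18 m/s. The sample is 10 + 10 = 20, which section 10.2 attributes to the time available. No SD, alpha, power or expected gain is given, so there is no calculation to reproduce. The attribution argument itself needs no figures.

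**Step 1: what each contrast contains.** Write the mean change as *g + b + s*, where *g* is background gain (other therapy, recovery, repeat testing), *b* is the effect of doing the balance programme at all, and *s* is any extra effect of the individual setting.

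- Individual arm: *g + b + s*
- Group arm: *g + b*
- Difference between arms: *s*

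The within-arm changes give only the sum *g + b*. With no arm at *b* = 0, *b* cannot be separated from *g* by any analysis. The difference between arms removes both in expectation, because randomisation makes *g* common to the two arms.

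**Step 2: how much other therapy runs alongside.** At 3 or 4 therapies on each of 5 weekdays for 3 weeks, there are 3 × 5 × 3 = 45 to 4 × 5 × 3 = 60 other units. The six balance units are 6/(6 + 45) = 11.8% to 6/(6 + 60) = 9.1% of all units. This counts sessions, not minutes, and some of the other therapies, such as speech therapy, are not aimed at gait.

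**Step 3: individual patients passing 0.18 m/s when *b* = *s* = 0.** Assume change is normal with mean *g* and SD *σ*. Neither value is in the documents, so a range is shown.

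P(patient reaches 0.18) = 1 − Φ((0.18 − *g*)/*σ*)

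| σ (m/s) | g = 0 | 0.10 | 0.15 | 0.20 | 0.25 |
|---|---|---|---|---|---|
| 0.15 | 11.5% | 29.7% | 42.1% | 55.3% | 68.0% |
| 0.20 | 18.4% | 34.5% | 44.0% | 54.0% | 63.7% |
| 0.25 | 23.6% | 37.4% | 45.2% | 53.2% | 61.0% |

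For *g* from 0.10 to 0.25 the range is 29.7% to 68.0%.

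**Step 4: the pooled mean of 20 passing 0.18 m/s, same model.**

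P(mean reaches 0.18) = 1 − Φ((0.18 − *g*)/(*σ*/√20))

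| σ (m/s) | g = 0 | 0.10 | 0.15 | 0.20 | 0.25 |
|---|---|---|---|---|---|
| 0.15 | <0.1% | 0.9% | 18.6% | 72.5% | 98.2% |
| 0.20 | <0.1% | 3.7% | 25.1% | 67.3% | 94.1% |
| 0.25 | 0.1% | 7.6% | 29.6% | 64.0% | 89.5% |

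The mean-level result is set almost wholly by the assumed background gain.

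**Step 5: precision of the contrast the design does support.** With 10 per arm, the approximate 95% half-width for the difference in mean change is 1.96 × *σ* × √(2/10). This gives 0.131, 0.175 and 0.219 m/s for *σ* = 0.15, 0.20 and 0.25. A t quantile would make these slightly wider. The estimate is imprecise but interpretable.

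**The case against.** The strongest reply is that the between-arm comparison is already the stated aim. The second sentence of 4.2, the synopsis, 3.1 and 10.1 all say so, and 5.1 repeats the question. On this view only a loose phrase in 4.2 is at fault. That is largely right, and it limits the point: the question, the hypothesis and the randomised contrast are sound in this respect. The causal phrase nevertheless stands first in the primary goal, the only threshold for change in speed is attached to improvement as such, and section 10 names no usable between-arm estimate.

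Four stronger readings are tempting, and the documents do not support them.

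- *The trial would declare success when training does nothing.* There is no test or decision rule. Section 10.2 limits the sample to descriptive statistics and a sample size calculation, and 10.1 expects no more than a guess. The 18 cm/s is cited to a paper on clinically important change and stands beside an ideal speed for crossing a road. It can fairly be read as a patient-level benchmark.
- *The follow-up trial would be sized on 0.18 m/s.* Section 10 says the calculation will use the data obtained. No passage proposes 0.18 m/s as a between-arm difference.
- *Patients are in early recovery, so a large background gain is certain.* Eligibility sets no time since stroke, section 7 also admits patients already on the ward, and section 11 gives stays from four weeks to about five months.
- *The individual-versus-group comparison is invalid.* Background gain is common to both arms in expectation, so it does not bias that comparison.

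**Conclusion.** The point holds as a limit on attribution. The improvement claimed in the first half of 4.2, and the 18 cm/s in 5.1 when read as before-after gain, cannot be credited to balance training, because both arms get the same exercises on top of full rehabilitation. This conclusion rests on the design alone.

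Its practical size does depend on assumptions. With no training effect, background gains of 0.10 to 0.25 m/s and SDs of 0.15 to 0.25 m/s, about 30% to 68% of individual patients would reach 0.18 m/s. These are patient-level percentages and should not be read as the chance that the trial as a whole passes. For the pooled mean, a background gain of 0.10 m/s gives under 8% at every SD considered, and a gain of zero gives about 0.1% or less. A misleading pass at mean level is therefore likely only if background gain approaches or exceeds 0.18 m/s.

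The correction is worth making. It removes a conclusion the design cannot support, and it supplies the between-arm estimate that section 10 lacks.

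**What to change.** - **4.2:** delete the attribution of improvement to balance training as a goal. Keep the individual-versus-group comparison as the primary goal.
- **4.2, 5.1 and section 10:** define the primary estimate as the individual-minus-group difference in change in walking speed (day after the last unit minus day before the first), reported with its 95% confidence interval. It replaces the odds ratio that has no defined binary outcome.
- **5.1 and section 10:** report mean change within each arm, and the number reaching 0.18 m/s in each arm, as a description of change during rehabilitation. State that neither is an effect of balance training.

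The cost is small. No new data or visits are needed. The authors give up a statement that the training works, which would require an arm without it. Because the change touches target criteria and the statistical evaluation, section 2.8 makes it a substantial amendment that needs ethics committee approval before use.
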